### **13.1 Protocol Amendments**

Any change to the protocol can only be made in a written protocol amendment that must be approved by Novartis, Health Authorities where required, and the IRB/IEC prior to implementation.

Amendments that are intended to eliminate an apparent immediate hazard to subjects may be implemented immediately, provided the Health Authorities are subsequently notified by protocol amendment and the reviewing IRB/IEC is notified.

Notwithstanding the need for approval of formal protocol amendments, the investigator is expected to take any immediate action required for the safety of any subject included in this study, even if this action represents a deviation from the protocol. In such cases, the reporting requirements identified in [Section 9](#) (Safety Monitoring) must be followed and the Study Lead informed.

## 15 Appendix 1: Liver Event definitions and follow-up requirements

**Table 15-1 Liver Event definitions**

Definition	Thresholds
Potential Hy's law cases	

ALT or AST <math>> 3 \times \text{ULN}</math> and TBL <math>> 2 \times \text{ULN}</math> without initial increase in ALP to <math>> 2 \times \text{ULN}</math>

ALT or AST elevation with coagulopathy	

ALT or AST <math>> 3 \times \text{ULN}</math> and INR <math>> 1.5</math> (in the absence of anticoagulation)

ALT or AST elevation accompanied by symptoms	

ALT or AST <math>> 3 \times \text{ULN}</math> accompanied by (general) malaise, fatigue, abdominal pain, nausea, or vomiting, or rash, or eosinophilia

Isolated ALT or AST elevation	

ALT or AST <math>> 8 \times \text{ULN}</math>

<math>5 \times \text{ULN} < \text{ALT/AST} \leq 8 \times \text{ULN}</math>

<math>3 \times \text{ULN} < \text{ALT/AST} \leq 5 \times \text{ULN}</math>

Isolated ALP elevation	

ALP <math>> 2 \times \text{ULN}</math> (in the absence of known bone pathology)

Others	

Any clinical event of jaundice (or equivalent term)

Any adverse event potentially indicative of liver toxicity

**Table 15-2 Actions required for Liver Events**

Criteria	Actions required
Potential Hy's Law case	

Discontinue the study treatment immediately

Hospitalize, if clinically appropriate

Establish causality

Complete CRFs per liver event guidance

ALT or AST elevation with coagulopathy	
ALT or AST elevation accompanied by symptoms	
Isolated ALT or AST elevation $> 8 \times \text{ULN}$	
Jaundice	
Isolated ALT or AST elevation $> 5$ to $\leq 8 \times \text{ULN}$	

If confirmed, consider interruption or discontinuation of study drug

If elevation persists for more than 2 weeks, discontinue the study drug

Establish causality

Complete CRFs per liver event guidance

Isolated ALT or AST elevation $> 3$ to $\leq 5 \times \text{ULN}$ (patient is asymptomatic)	

Monitor liver chemistry tests two or three times weekly

Criteria	Actions required
Isolated ALP elevation	

• Repeat liver chemistry tests within 48-72 hours

• If elevation is confirmed, measure fractionated ALP; if >50% is of liver origin, establish hepatic causality

• Complete CRFs per liver event guidance

Any AE potentially indicative of liver toxicity	

• Consider study treatment interruption or discontinuation

• Hospitalize if clinically appropriate

• Complete CRFs per liver event guidance

**Table 15-3      Exclusion of underlying liver disease**

Disease	Assessment
Hepatitis A, B, C, E	

• IgM anti-HAV; HBSAg, IgM anti-HBc, HBV DNA; anti-HCV, HCV RNA, IgM & IgG anti-HEV, HEV RNA

CMV, HSV, EBV infection	

• IgM & IgG anti-CMV, IgM & IgG anti-HSV; IgM & IgG anti-EBV

Autoimmune hepatitis	

• ANA & ASMA titers, total IgM, IgG, IgE, IgA

Alcoholic hepatitis	

• Ethanol history, gGT, MCV, CD-transferrin

Nonalcoholic steatohepatitis	

• Ultrasound or MRI

Hypoxic/ischemic hepatopathy	

• Medical history: acute or chronic CHF, hypotension, hypoxia, hepatic venous occlusion. Ultrasound or MRI.

Biliary tract disease	

• Ultrasound or MRI, ERCP as appropriate.

Wilson disease	

• Caeruloplasmin

Hemochromatosis	

• Ferritin, transferrin

Alpha-1-antitrypsin deficiency	

• Alpha-1-antitrypsin

## 16 Appendix 2: Specific Renal alert criteria and actions

**Table 16-1 Specific Renal alert criteria and actions**

Criteria	Action required
Serum creatinine (sCr) increase 25 – 49% compared to baseline	

Consider causes and possible interventions

Follow up within 2-5 days

Serum creatinine increase $\geq$ 50%	

Consider causes and possible interventions

Repeat assessment within 24-48h if possible

Consider drug interruption or discontinuation unless other causes are diagnosed and corrected

Consider hospitalization and specialized treatment

Protein-creatinine or albumin-creatinine ratio increase $\geq$ 2-fold or new onset dipstick proteinuria $\geq$ 1+ or Albumin-creatinine ratio (ACR) $\geq$ 30 mg/g or $\geq$ 3 mg/mmol; or Protein-creatinine ratio (PCR) $\geq$ 150 mg/g or $>15$ mg/mmol	

Consider causes and possible interventions

Assess serum albumin & serum protein

Repeat assessment to confirm

Consider drug interruption or discontinuation unless other causes are diagnosed and corrected

New onset glucosuria on urine dipstick (unless related to concomitant treatment, diabetes)	
Assess & document:
 

Blood glucose (fasting)

Serum creatinine

Urine albumin-creatinine ratio

New hematuria on dipstick	
Assess & document:
 

Urine sediment microscopy

Assess sCr and urine albumin-creatinine ratio

Exclude infection, trauma, bleeding from the distal urinary tract/bladder, menstruation

Consider bleeding disorder

Additional specialized assessments are available to assess renal function or renal pathology. (Note: In exceptional cases when a nephrologist considers a renal biopsy, it is strongly recommended to make specimen slides available for evaluation by Novartis to potentially identify project-wide patterns of nephrotoxicity.)

Whenever a renal event is identified, a detailed subject history and examination are indicated to identify, document and potentially eliminate risk factors that may have initiated or contributed to the event:

- Blood pressure assessment (after 5 min rest, with an appropriate cuff size)
- Signs and symptoms such as fever, headache, shortness of breath, back or abdominal pain, dysuria, hematuria, dependent or periorbital edema
- Changes in blood pressure, body weight, fluid intake, voiding pattern, or urine output
- Concomitant events or procedures such as trauma, surgical procedures, cardiac or hepatic failure, contrast media or other known nephrotoxin administration, or other potential causes of renal dysfunction, e.g., dehydration, hemorrhage, tumor lysis

**Table 16-2 Follow-up of renal events**

Action	Follow up
Assess*, document and record in the Case Report Form (CRF) or via electronic data load. Review and record possible contributing factors to the renal event (co-medications, other co-morbid conditions) and additional diagnostic procedures (MRI etc) in the CRF.	

• Urine dipstick and sediment microscopy

• Blood pressure and body weight

• Serum creatinine, electrolytes (sodium, potassium, phosphate, calcium), bicarbonate and uric acid

• Urine output

 
• Event resolution: (sCr within 10% of baseline or protein-creatinine ratio within 50% of baseline)

Monitor subject regularly (frequency at investigator's discretion) until:	
or
 

• Event stabilization: sCr level with <math>\pm 10\%</math> variability over last 6 months or protein-creatinine ratio stabilization at a new level with <math>\pm 50\%</math> variability over last 6 months.

\*Urine osmolality: in the absence of diuretics or chronic kidney disease this can be a very sensitive metric for integrated kidney function that requires excellent tubular function. A high urinary osmolality in the setting of an increase in sCr will point toward a "pre-renal" cause rather than tubular toxicity.

## 1 Introduction

### 1.1 Scope of document

The RAP documents contain detailed information to aid the production of Statistics & Programming input into the Clinical Study Report (CSR) for trial “**CACZ885X2205**”.

The Statistical analysis plan (SAP) describes the implementation of the statistical analysis planned in the protocol.

Tables, Figures, Listings (TFL) details the presentation of the data, including shells of summary tables, figures and listings, and Programming Datasets Specification (PDS) contains programming specifications e.g. for derived variables and derived datasets, to support the creation of CSR outputs.

### 1.2 Study reference documentation

Final study protocol is available at the time of finalization of Statistical Analysis Plan.

### 1.3 Study objectives

#### ***1.3.1. Primary objective(s)***

Primary objective(s)	Endpoints related to primary objectives

To compare the effect of ACZ885 versus placebo on the clinical disease activity of sarcoidosis patients as measured by the change from baseline in the percent predicted forced vital capacity (FVC) at week 24

	

Change from baseline in percent predicted FVC at week 24.

#### ***1.3.2. Secondary objective(s)***

Secondary objective(s)	Endpoints related to secondary objective(s)

To determine the effect of ACZ885 on decreasing the maximum standardized uptake value (SUVmax) [F-FDG-PET SUVmax in nodules (nodular uptake regions) after 12 weeks of treatment, compared to placebo

	

Percent change from initial scan in [F-FDG-PET SUVmax at week 12

To determine the effect of ACZ885 versus placebo on other parameters of pulmonary function testing (i.e., absolute FVC, FEV1, FEV1/FVC, FEV3, FEV6, FEF25-75, FEV3/FVC, 1- (FEV3/FVC), TLC, RV, RV/TLC, DLco and postbronchodilator FEV1/reversibility) in patients with

	

Lung function testing results at 24 weeks compared to baseline

sarcoidosis at 24 weeks compared to baseline	

To determine the effect of ACZ885 versus placebo on HRCT of patients with sarcoidosis at 24 weeks compared to initial HRCT scan as measured by side-by-side comparison by blinded reviewers and HRCT scoring

	

HRCT results at 24 weeks compared to HRCT initial scan measured by blinded reviewers and HRCT scoring

To determine the effect of ACZ885 versus placebo on the 6-minute walk test (6MWT) distance of patients with sarcoidosis at 12 and 24 weeks compared to baseline

	

6MWT results at week 12 and 24 compared to baseline

To determine the effect of ACZ885 on additional [F-18]FDG-PET outcomes (i.e., SUVmean, SUVpeak and volume of the lesions) after 12 weeks of treatment compared to placebo

	

Percent change from initial scan in additional [F-18]FDG PET outcomes at week 12

To assess the safety and tolerability of ACZ885 in patients with sarcoidosis as measured by adverse events (AEs)

	

Adverse events in patients taking ACZ885 compared to placebo

### **1.3.3. Exploratory objective(s)**

Corporate Confidential Information

Corporate Confidential Information

Corporate Confidential Information

#### 1.4 Study design and treatment

This is a subject- and investigator-blinded, randomized, placebo-controlled, parallel group, non- confirmatory study to assess the clinical efficacy of ACZ885 administered subcutaneously (s.c.) every four weeks for a total of 24 weeks.

The study will randomize approximately 38 patients with evidence of parenchymal involvement determined by HRCT and histologically proven, chronic pulmonary sarcoidosis of  $\geq 1$  year duration with persisting activity at baseline despite background therapy.

[figure not shown]

Figure 1-1: Study design scheme

#### 2 First interpretable results (FIR)

Corporate Confidential Information

Corporate Confidential Information

### **3      Interim analyses**

Corporate Confidential Information

Corporate Confidential Information

## 4 Statistical methods: Analysis sets

For all analysis sets, subjects will be analyzed according to the study treatment(s) received. In case(s) of miss-stratification, the real stratum will be used in the analysis.

The safety analysis set will include all subjects that received any study drug.

The PK analysis set will include all subjects with available PK data and no protocol deviations with relevant impact on PK data.

The PD analysis set will include all subjects that received any study drug and that have no protocol deviations with relevant impact on PD data.

For subjects for which the actual treatment received does not match the randomized treatment the treatment actually received will be used for the analysis.

**Table 4-1 Protocol deviation codes and analysis sets**

Category Deviation code	Text description of deviation	Data exclusion
Subjects are excluded from all (safety) analysis in case of these PDs:		Exclude subject completely from all (safety) analysis sets
INCL01	Deviation from inclusion criteria: Written informed consent was not obtained before any study assessment was performed	Yes
Subjects are excluded from PK analysis in case of these PDs:		Exclude subject from PK analysis set
INCL01	Deviation from inclusion criteria: Written informed consent was not obtained before any study assessment was performed	Yes

Category Deviation code	Text description of deviation	Data exclusion
Subjects are excluded from PD analysis in case of these PDs:		
INCL01	Deviation from inclusion criteria: Written informed consent was not obtained before any study assessment was performed	Exclude subject from PD analysis set Yes
Subjects are excluded from PD analysis after the PD date in case of these PDs:		
COMD01	Prohibited medication used	Exclude subject from PD analysis set after the date of the event Yes
Subjects are excluded from PK and PD analysis in case of these PDs:		
INCL01	Deviation from inclusion criteria: Written informed consent was not obtained before any study assessment was performed	Exclude subject from PK and PD analysis sets Yes

If updates to this table are needed, an amendment to the SAP needs to be implemented prior to DBL.

## 5 Statistical methods for Pharmacokinetic (PK) parameters

All subjects within the PK analysis set will be included in the PK data analysis.

### 5.1 Variables

The following pharmacokinetic parameter will be determined: ACZ885 serum concentration.

### 5.2 Descriptive analyses

ACZ885 serum concentration data will be listed by subject and visit/sampling time point.

Corporate Confidential Information

## 6 Statistical methods for Pharmacodynamic (PD) parameters

All subjects within the PD analysis set will be included in the PD data analysis.

## **6.1 Primary objective**

To compare the effect of ACZ885 versus placebo on the clinical disease activity of sarcoidosis patients as measured by the change from baseline in the percent predicted forced vital capacity (FVC) at week 24.

### **6.1.1 Variables**

The primary variable will be the change from baseline in percent predicted FVC after 24 weeks of treatment. The FVC is measured at screening, day 1, week 4, week 8, week 12, week 16, week 20 and week 24. Baseline is defined as day 1. At the visits (day 1 and week 24) where pre- and post-bronchodilation assessments are done, the pre-bronchodilation values are used.

### **6.1.2 Descriptive analyses**

The raw percent predicted FVC values will be listed by treatment, subject and visit/time and descriptive statistics of both the raw and change in percent predicted FVC will be provided by treatment and visit/time. Summary statistics will include arithmetic mean, SD, CV (arithmetic), median, minimum and maximum.

Graphical methods will be employed to show mean (SD) figures for change in percent predicted FVC.

### **6.1.3 Statistical model, assumptions and hypotheses**

The change from baseline in percent predicted FVC will be analyzed using a Bayesian model for repeated measurements. The model will investigate effects for treatment by time (included as a class variable) interaction, baseline by time interaction. Uninformative priors will be utilized to obtain the posterior estimates.

The posterior probability that ACZ885 is better than placebo in terms of change from baseline in percent predicted FVC at 24 weeks will be derived. If it is at least 90%, it will be considered a sign of efficacy of ACZ885 in increasing FVC after 24 weeks of treatment in this patient population.

Corporate Confidential Information

The primary analysis will include all available information in terms of measurements at all times. If missing measurements are missing at random, an analysis of the available data provides consistent estimates of model parameters. Alternative assumptions may be explored to investigate the robustness of the results under plausible non-missing at random situations.

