### 3        Investigational plan

#### 3.1      Study design

Figure 3-1      Study Design scheme

This is a 32-week, subject- and investigator-blinded, randomized, placebo-controlled, parallel-group, non-confirmatory study to assess the clinical efficacy of ACZ885 administered subcutaneously (s.c.) in 6 injections given 28 days apart (Figure 3-1). The study will randomize approximately 38 patients (targeting 30 completers) with evidence of parenchymal involvement and histologically proven, chronic pulmonary sarcoidosis of  $\geq 1$  year duration with persisting activity at baseline despite background therapy as determined by clinical history, radiologic evidence (e.g. HRCT, MRI or chest x-ray), spirometry and MMRC dyspnea scale assessments. Randomization will be stratified by positive PET parenchymal tracer uptake (yes/no). Acceptable background therapy includes a stable regimen of prednisone  $\leq 15$  mg/day and/or no more than one immune suppressive agent (i.e., methotrexate, azathioprine, leflunomide or hydroxychloroquine).

Re-screening of subjects may be allowed with the consultation of the Sponsor's medical expert.

For each subject, there will be a maximum 40-day screening period. Screening is valid for 40 days from the time of the first screening assessment. [F-18]FDG-PET/CT scans obtained locally at the study site within 8 weeks of randomization will be acceptable for baseline assessment prior to receiving the first injection of ACZ885. However, any prior [F-18]FDG-PET/CT imaging must also have been done without changes in treatment during the subsequent period leading up to study randomization.

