### **11.4.2 Statistical model, hypothesis, and method of analysis**

The change from baseline in percent predicted FVC will be analyzed using a Bayesian model for repeated measurements. The model will investigate effects for treatment by time (included as a class variable) interaction, baseline by time interaction and PET positivity (yes/no) prior to randomization. Uninformative priors will be utilized to obtain the posterior estimates.

The posterior probability that ACZ885 is better than placebo in terms of change from baseline in percent predicted FVC at 24 weeks will be calculated. If it is at least 90%, it will be considered a sign of efficacy of ACZ885 in increasing FVC after 24 weeks of treatment in this patient population.

At the interim analysis, the posterior probability that ACZ885 is worse than placebo in terms of change from baseline in percent predicted FVC at week 12 will be calculated. If it is at least 60%, the study may be stopped for futility.

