## 11.5 Analysis of secondary variable(s)

### 11.5.1 Efficacy / Pharmacodynamics

#### 11.5.1.1 [F-18]

The [F-18]FDG-PET/CT imaging data will be analyzed to identify the max standardized uptake values in the following categories:

- A maximum of 5 focal nodal uptake regions (mediastinal, hilar)
- A maximum of 5 focal regions of uptake in lung parenchyma
- A maximum of 5 extra-thoracic focal uptake regions on the whole body scan

[F-18]FDG-PET/CT mean

- A region of lung parenchyma, unaffected by focal lesion uptake

The mean of the SUVmax (resp. SUVmean) for each category will be taken to obtain one SUVmax value (resp. SUVmean) per patient / time point / category.

The mean percent change from baseline in SUVmax in the nodules after 12 weeks of treatment will be analyzed using ANCOVA with baseline SUVmax as a covariate and treatment and PET positivity (yes/no) as factors.

The same analysis as for the percent change from baseline in SUVmax in the nodules will be performed for the percent change from baseline in SUVmax in the lung parenchyma and the extra-thoracic regions, where available. It will also be repeated for SUVmean in the parenchyma.

The percentage of patients with at least 50% reduction of SUVmax in nodules will be analyzed via logistic regression with baseline SUVmax as a covariate and treatment and PET positivity (yes/no) as factors.

Also the change in the individual lung nodules will be examined, using a discretized scale of complete response (CR), partial response (PR), stable disease (SD) and progressive disease (PD) as in the oncology European Organization for Research and Treatment of Cancer criteria for [F-18]FDG-PET/CT. The proportion of individual responders and non-responders will be determined, based on PET. Patients who discontinue for lack of efficacy will be treated as a separate category in this summary.

The correlation between changes from initial FDG-PET scan in SUVmax and changes from baseline in FVC, FEV1, COAs, 6MWT distance will be assessed with graphical methods.

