### **6.1.5 Sensitivity analyses**

A sensitivity analysis will be performed on the primary endpoint adding PET positivity (yes/not) prior to randomization a factor. The same analysis as defined in Section 6.1.3 will be performed, and adding PET positivity as a covariate in the model.

A further sensitivity analysis may be performed using an LOCF imputation for missing values. The main purpose of this analysis will be the investigation of potential bias, caused by subjects excluded from the analysis due to prohibited concomitant medication use (as concomitant medication increase is primarily due to poor response). However, the analysis will not be restricted to these subjects. A summary of prohibited medication incidence (as defined by the Protocol Deviations database), will be produced which will present the number of subjects with COMD01 deviations and time to first COMD01 deviation by treatment group, this summary will serve to decide whether the LOCF analysis will be performed.

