### **6.2.3 Statistical model, assumptions and hypotheses**

#### **[F-18]FDG-PET/CT**

The mean percent change from baseline in SUVmax in the nodules at week 12 will be analyzed using ANCOVA with baseline SUVmax as a covariate and treatment as factor.

The same analysis as for the percent change from baseline in mean SUVmax in the nodules will be performed for the percent change from baseline in SUVmax in the lung parenchyma and the extra-thoracic regions, where available, at week 12. It will also be repeated for SUVmean in the parenchyma.

The percentage of patients with at least 50% reduction of SUVmax in nodules will be analyzed via logistic regression with baseline SUVmax as a covariate and treatment and PET positivity (yes/no) prior to randomization as factors.

The same sensitivity and subgroup analyses as the primary may also be performed, if deemed necessary.

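### SAP 6.1.3 drops PET positivity, the only named randomisation stratum, from the primary model set in Protocol 11.4.2, so the same 90% rule is tied to two different models

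*SAP*

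**What the plan says.** **Primary model.** Protocol 11.4.2 lists treatment by time and then "interaction, baseline by time interaction and PET positivity (yes/no) prior to randomization"; the protocol synopsis names the same terms. SAP 6.1.3 stops one term earlier: "The model will investigate effects for treatment by time (included as a class variable) interaction, baseline by time interaction". Both then call a posterior probability of at least 90% in favour of ACZ885 at week 24 a sign of efficacy.

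**Where PET went.** SAP 6.1.5 says: "A sensitivity analysis will be performed on the primary endpoint adding PET positivity (yes/not) prior to randomization a factor". The protocol's primary model has therefore become the SAP's sensitivity analysis, while Protocol 11.4.4 lists sensitivity analyses as not applicable. SAP 1.1 gives the document's purpose: "The Statistical analysis plan (SAP) describes the implementation of the statistical analysis planned in the protocol".

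**Status of PET in the design.** Protocol 3.1 stratifies randomisation on parenchymal tracer uptake (yes/no), and Protocol 6.3 names no other factor. The imaging rationale under Protocol 2.2 says that later analyses will also stratify on it. SAP section 4 says the true stratum is to be used in the analysis after mis-stratification.

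**Secondary models.** For nodal SUVmax, Protocol 11.5.1.1 has "analyzed using ANCOVA with baseline SUVmax as a covariate and treatment and PET positivity (yes/no) as factors", whereas SAP 6.2.3 has "analyzed using ANCOVA with baseline SUVmax as a covariate and treatment as factor". The same SAP section keeps the term in the responder model: "analyzed via logistic regression with baseline SUVmax as a covariate and treatment and PET positivity (yes/no) prior to randomization as factors". For HRCT, Protocol 11.5.1.2 names treatment and PET positivity. The SAP 6.2.3 sentence refers to factors in the plural but names only treatment, followed by a stray reference to screening.

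**The concern.** The trial has one formal efficacy decision: whether the posterior probability reaches 90%. The documents attach it to two models. If the two probabilities fall on either side of 90%, each answer can be called pre-specified, and nothing visible says which governs.

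The omitted term is also not an arbitrary covariate. It is the factor on which allocation is balanced, and the protocol's rationale is that PET-positive patients are more likely to improve. Leaving a prognostic stratum out of the model after stratifying on it makes the posterior wider than the design warrants, which costs some power. The error rate does not rise. The secondary models show no consistent rule either, since within SAP 6.2.3 PET positivity is dropped from the SUVmax ANCOVA and kept in the logistic model.

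**Working it through.** **1. Is the omission real?** The model sentence in SAP 6.1.3 is complete, and the redacted block comes after the 90% rule. SAP 6.1.5 then adds PET positivity to the 6.1.3 model, which would be pointless if it were already there. The redaction could hide a reason, but not the term.

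**2. The plan's own figure.** Inputs from Protocol 11.7: 15 per group at week 24, SD 9, true effect 7, 10% false-positive rate. With a flat prior, a posterior probability of at least 90% is equivalent to a one-sided 10% test.

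- Standard error = 9 × √(2/15) = 3.286; 7 / 3.286 = 2.130
- Power = Φ(2.130 − 1.2816) = 80.2% (79.3% with the t distribution), against a stated figure of about 80%
- With a true difference of 0: 10.0%, as stated

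The stated figures reproduce. They use a single SD and no covariates, so they do not show which model was intended.

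**3. Effect of omitting PET when it is prognostic.** The documents give neither the PET-positive share p nor the difference D between strata in FVC change. Both are assumed here. Total SD is held at 9, with exact balance within strata.

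- Residual SD: r = √(81 − p(1−p)D²)
- Without PET, the model's SD estimate stays near 9 while the treatment estimate varies with r, so the effective cut-off is c = 1.2816 × 9 / r
- False-positive rate without PET = 1 − Φ(c)
- Power without PET = Φ(7 / (r√(2/15)) − c); with PET = Φ(7 / (r√(2/15)) − 1.2816)

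Worked case, D = 5 and p = 0.5: r = √(81 − 6.25) = 8.646; c = 1.334; false-positive rate 9.1%; 7 / (8.646 × 0.3651) = 2.217; power Φ(0.883) = 81.1% without PET and Φ(0.936) = 82.5% with it.

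| D | p | False-positive rate without PET | Power without PET | Power with PET |
|---|---|---|---|---|
| 0 | any | 10.0% | 80.2% | 80.2% |
| 5 | 0.5 | 9.1% | 81.1% | 82.5% |
| 5 | 0.7 | 9.3% | 81.0% | 82.1% |
| 7 | 0.5 | 8.2% | 82.1% | 84.9% |
| 7 | 0.7 | 8.5% | 81.8% | 84.1% |

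**4. How often do the two models disagree?** Simulation of the week-24 change only: flat-prior t posterior, 15 per arm, 8 or 10 PET-positive per arm, 100,000 trials per case.

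| D | Opposite decisions, true effect 0 | Opposite decisions, true effect 7 |
|---|---|---|
| 0 | 0.4% | 0.7% |
| 5 | 1.0-1.1% | 1.7-1.8% |
| 7 | 1.7-1.9% | 2.7-3.1% |

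A more extreme D of 9, with 16 to 24 of 30 patients PET-positive, gives simulated power of 81.1-82.1% without PET against 84.4-87.0% with it, and disagreement of up to about 5%.

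**5. If PET modifies the treatment effect.** Assume benefit in PET-positive patients only, averaging 7 overall, so 7 × 15/8 = 13.1 or 7 × 15/10 = 10.5 points in that stratum. Residual SD is 9 here, so these rows are not directly comparable with step 3.

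| Untreated difference, PET-positive minus PET-negative | PET-positive per arm | Power without PET | Power with PET |
|---|---|---|---|
| 0 | 8 of 15 | 74.1% | 76.6% |
| 0 | 10 of 15 | 76.5% | 77.9% |
| −5 | 8 of 15 | 76.6% | 76.6% |
| −5 | 10 of 15 | 77.8% | 77.7% |

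In the last two rows, adjusting for PET gains nothing.

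**The case against.** The best reply is that little is at stake. The trial is declared non-confirmatory, 90% is only a sign of efficacy, the false-positive rate is not inflated, and SAP 6.1.5 commits to the PET-adjusted model, so both posterior probabilities will be reported. That limits the size of the problem. It does not say which probability decides.

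The omission may also be deliberate: a sensitivity analysis is built around it, and a reason could lie in the redacted part of 6.1.3 or in 6.1.4. That stands, which is why the claim is only that no reason is visible, and why declaring the change is an acceptable alternative.

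The interim is a fair point too. Protocol 6.4 allows the statistician and sponsor team to be unblinded at the interim, and SAP section 3 is redacted, so a reader cannot tell whether interim data preceded the SAP. An amendment should state this.

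On the numbers, step 3 uses a normal approximation. The t posterior gives powers about 1 point lower, with the same 1 to 3 point gain. All cases ignore the FVC baseline and the repeated measures, and assume that balance within strata survives the loss from 38 randomised to 30 completers. The 5 to 7 point differences are assumptions. Finally, the HRCT sentence looks like an editing slip, not a decision to drop PET; it still has to be corrected before it can be programmed.

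**Conclusion.** The concern holds. The protocol and the SAP specify different primary models for the same 90% rule, and the missing term is the only named randomisation stratum. Under the assumed 5 to 7 point stratum difference, the SAP model is slightly conservative (false-positive rate 8.2-9.3% against 10%) and gives up about 1 to 3 points of power; the decision changes in about 1 to 3% of trials. With no PET effect on FVC the average cost is nil. The sample size calculation is sound. The case for change is a single governing model that matches the protocol and the stratified design, not a faulty error rate. The change should be made, but the trial does not fail without it.

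**What to change.** Amend the SAP before unblinding, and state in the amendment whether anyone involved had seen unblinded interim data.

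1. **SAP 6.1.3:** restore PET positivity (yes/no) as a factor, as in Protocol 11.4.2, and state that this model's posterior probability decides the 90% rule. Make the model without PET the sensitivity analysis in 6.1.5. The FEV1, FEV3 and FEV6 models in 6.2.3 are defined by reference to 6.1.3 and will inherit the term.
2. **SAP 6.2.3, PET:** restore the factor in the nodal SUVmax ANCOVA, and in the extra-thoracic SUVmax and parenchymal SUVmean ANCOVAs where both strata contribute data. Leave it out of the ANCOVA for focal parenchymal SUVmax. If PET positivity means the stratum defined in Protocol 3.1, it would be constant or nearly so there. Say so explicitly, because Protocol 11.5.1.1 asks for the same analysis in that region.
3. **SAP 6.2.3, HRCT:** correct the sentence to name treatment and PET positivity, as in Protocol 11.5.1.2.

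If the omission from 6.1.3 was intended, record it with its reason as a change from the protocol and state which model governs.

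The cost is a SAP amendment, small edits to model code and table shells, and one degree of freedom per model. The stratum is already collected, and the PET-adjusted FVC model is already planned in 6.1.5.
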